## SECTION I: RESEARCH PLAN

1. **Statement of Purpose:** State the scientific aim(s) of the study, or the hypotheses to be tested.

The specific aims of Sub-study #1 are:

Specific Aim #1: DEVELOPMENT: We will update our current Invite Only VR prototype into a polished videogame intervention using input from 4 focus groups of 5 adolescents each (n = 20), aged 12-17 and the extant literature. These focus groups will inform the development of the VR videogame intervention, *Invite Only VR*, for e-cigarette prevention among teens.

Specific Aim #2: EVALUATION: Conduct a pilot randomized controlled trial with 300 teens ages 11-15 comparing the Invite Only VR intervention vs. an attention/control non-health-related VR videogame, collecting assessment data at baseline, post-gameplay, three months and six months to determine:

- a. the preliminary impact of the intervention on knowledge, intentions, perceptions, attitudes, social norms, self-efficacy and behaviors related to: i) initiation of e-cigarette use, ii) e-cigarette use cessation.
- b. the intervention's acceptability and feasibility by collecting quantitative and qualitative data on teens' satisfaction and gameplay experience of the intervention.
- c. preliminary evidence of the impact of *Invite Only VR* on players' perception and experience of social pressure and social norm development.

The specific aim for Sub-study #2 is

Specific Aim #1: EVALUATION: Conduct a quasi-experimental effectiveness trial of the Invite Only VR intervention using a pre-post study design with 400 teens ages 11-15, collecting assessment data at baseline and post-gameplay to determine:

- a. the preliminary impact of the intervention on knowledge, intentions, perceptions, attitudes, social norms, self-efficacy and behaviors related to: i) initiation of e-cigarette use, ii) e-cigarette use cessation.
- b. the intervention's acceptability and feasibility by collecting quantitative on teens' satisfaction and gameplay experience of the intervention.

2. **Probable Duration of Project:** State the expected duration of the project, including all follow-up and data analysis activities.

2 years

3. **Background:** Describe the background information that led to the plan for this project. Provide references to support the expectation of obtaining useful scientific data.

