**Conduct focus groups to gather data to inform refinement of the current videogame prototype, *Invite Only VR*.**

We will conduct 4 focus groups (5 adolescents each) to collect feedback on the game content, art, narrative, and characters, and gameplay mechanics. We will use visual tools (e.g., storyboards, pictures) to facilitate the discussions. We will conduct the focus groups according to standard dual-facilitator procedures. We anticipate that 4 focus groups will be adequate to achieve thematic saturation. The focus groups will be conducted such that ideas and themes from one discussion inform discussion topics and prompts used in the next focus group. Participants will be compensated with a gift card for \$25. Audio recordings of each session will be transcribed, reviewed and discussed by the research team to refine the videogame intervention. As a part of the game development, with parental permission we will invite selected students to the Yale recording studio on campus to provide voices for the videogame characters.

**Conduct randomized controlled trial:** We will enroll 300 adolescents to test *Invite Only VR* using a pre/post design to evaluate the preliminary efficacy of the videogame prototype, *Invite Only VR*. Participants will be randomly assigned to play either Invite Only VR (n=115), or receive standard care as usual (n=115). Participants will accumulate between 1.5-2 hours of game play over 2 sessions (approximately one week, meeting twice). Participants will play the *Invite Only VR* game on a VR headset for 45 mins to 1 hour, one to two times per week for 2 weeks (to accumulate up to 1.5 - 2 hours of gameplay). This total duration and number of sessions is consistent with those found in effective smoking prevention interventions among adolescents and with the amount of time adolescents play videogames. Participants will have a 10 min break in the middle of each session and will be instructed that they may take additional breaks as needed.

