**Measures.** We will collect data on participant demographics at baseline. At baseline and immediately after gameplay, and again at 3 and 6 months post gameplay, we will collect data on intentions to initiate smoking, self-efficacy for refusing offers of e-cigarettes and other tobacco products, perceived social norms related to smoking, attitudes about smoking, and smoking behavior using validated questionnaires. Finally, we will assess satisfaction with game play and acceptability and feasibility of the intervention by collecting self-report data at the end of the game play period. All assessments will be conducted via face-to-face interviews with a research assistant and each adolescent.

**Study locations.** For the focus groups and pilot-testing, the study will take place at one of the after-school programs with which the play2PREVENT Lab has ongoing partnerships including but not limited to: Wilbur Cross High School (which serves 1300 students from 9th to 12th grade), Hamden Youth Center (which serves roughly 75 adolescents in the 6th through 12th grade, and the Milford Middle School District (which serves 1300 students the majority of whom are between the ages of 11 and 14), and LEAP (which serves over 1000 children between the ages of 7-18). For the randomized controlled trial, we will enroll students from the Milford Middle School District between the ages of 11-15.

**Participants, screening, and consent.** In collaboration with community program staff, we will discuss the study with interested parents and adolescents and collect eligibility screening data. If the participant is eligible and interested we will proceed with the consent procedures that will differ by phase of the research. For focus groups, we will give information sheets to the adolescents and to their parents describing the purpose of and protocol for the focus groups. Parents who do not wish for their children to participate will contact the project director. No forms will be signed for focus groups. For the randomized controlled trial, we will obtain written, informed assent (adolescent) and consent (parent).

In addition to paper forms for parental consent for participation in the randomized controlled study, we will also provide a web-based form for parents to review and electronically sign through Yale Qualtrics.

For Sub-study #2:

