To minimize possible physical risks associated with the project, per the health and safety manual for the virtual reality headsets, participants will not be allowed to use the virtual reality headsets while they are tired, sleep impaired, if they have digestive problems, are under emotional stress or anxiety or suffering from a cold, flu, headache, migraine or earache. Additionally, participants using the virtual reality headsets will be required to take a 10-15 min break for every 30 mins of game play.

Furthermore, throughout their gameplay experience, to help minimize risk participants utilizing the VR headsets will be asked about how they are physically feeling. If the participant's answer indicates that they are experiencing any of the adverse physical symptoms, the research staff will immediately stop gameplay.

In the unlikely event that a participant involved with the study experiences a serious medical or psychological complication, that requires further attention, this would be reported to [name] who will then determine if further consultation is required without divulging the name of the individual, if this appeared appropriate and necessary. [name] would then be responsible for ensuring that the needs of the individual were addressed.

12. **Data and Safety Monitoring Plan:** Include an appropriate Data and Safety Monitoring Plan (DSMP) based on the investigator's risk assessment stated below. (Note: the HIC will make the final determination of the risk to subjects.)
- a. What is the investigator's assessment of the overall risk level for subjects participating in this study? Minimal risk
  - b. If children are involved, what is the investigator's assessment of the overall risk level for the children participating in this study? Minimal risk
  - c. Include an appropriate Data and Safety Monitoring Plan. Examples of DSMPs are available here <http://your.yale.edu/policies-procedures/forms/420-fr-01-data-and-safety-monitoring-plans-templates> for
    - i. Minimal risk
    - ii. Greater than minimal

The principal investigator is responsible for monitoring the data, assuring protocol compliance, and conducting the safety reviews quarterly. During the review process, the principal investigator will evaluate whether the study should continue unchanged, require modification/amendment, or close to enrollment.

The principal investigator or the Human Investigative Committee (HIC) have the authority to stop or suspend the study or require modifications.

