#### SECTION IV: PROTECTION OF RESEARCH SUBJECTS

##### Confidentiality & Security of Data:

1. What protected health information (medical information along with the HIPAA identifiers) about subjects will be collected and used for the research? *Name, Address, Telephone Number, Email Address*
2. How will the research data be collected, recorded and stored? All data collected from the assessments will be entered directly into the secure web-based system, OnCore, which is Yale's enterprise-wide data management system. Research staff will enter the data into the OnCore system. For the more sensitive information collected, the participant will enter these data. To assess acceptability and feasibility, directly following completion of the intervention, we will collect quantitative and qualitative data on the intervention participants' experiences of the game intervention.
3. How will the digital data be stored?  CD  DVD  Flash Drive  Portable Hard Drive  Secured Server  
 Laptop Computer  Desktop Computer  Other
4. What methods and procedures will be used to safeguard the confidentiality and security of the identifiable study data and the storage media indicated above during and after the subject's participation in the study?

Data will be stored in Yale's secured online data collection system, OnCore. Paper assessments will be kept in a locked filing cabinet in the PI's office.

All portable devices must contain encryption software, per University Policy 5100. If there is a technical reason a device cannot be encrypted please submit an exception request to the Information Security, Policy and Compliance Office by clicking on url <http://its.yale.edu/egrc> or email [[contact]](mailto:[contact])

5. What will be done with the data when the research is completed? Are there plans to destroy the identifiable data? If yes, describe how, by whom and when identifiers will be destroyed. If no, describe how the data and/or identifiers will be secured. Data collected in the study will reside in our computerized database and electronic storage mechanisms. All data analyses will be performed under approved HIC protocols.
6. If appropriate, has a Certificate of Confidentiality been obtained? *Write here*

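### Feasibility and acceptability rest on end-of-play self-report alone: this cannot show whether the planned play was delivered, and the plan does not say whether early stoppers are asked

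*Combined protocol and SAP*

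**What the plan says.** Aim 2b of Sub-study #1 (Section I, item 1) is to determine "the intervention's acceptability and feasibility by collecting quantitative and qualitative data on teens' satisfaction and gameplay experience of the intervention". Aim 1b of Sub-study #2 is the same but for quantitative data only. For both sub-studies the Measures paragraph in Section I, item 4 gives one method: the team will assess "acceptability and feasibility of the intervention by collecting self-report data at the end of the game play period". Section IV, Confidentiality & Security of Data, item 2 adds a time point: "To assess acceptability and feasibility, directly following completion of the intervention, we will collect quantitative and qualitative data".

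On exposure, the Sub-study #1 trial description states: "Participants will accumulate between 1.5-2 hours of game play over 2 sessions". Sub-study #2 has the same 1.5-2 hour total, played in one or two sittings of 45-60 minutes.

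Section I, item 11 (Minimizing Risks) foresees interrupted and missed play. During play, "participants utilizing the VR headsets will be asked about how they are physically feeling". It continues: "If the participant's answer indicates that they are experiencing any of the adverse physical symptoms, the research staff will immediately stop gameplay". It also says that "participants will not be allowed to use the virtual reality headsets while they are tired", and lists several kinds of illness or distress alongside tiredness. It does not say what then happens to the end-of-play assessment.

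Two other places bear on the point. The safety monitoring plan (item 12) promises records of research activities and of completed assessments. Statistical Considerations (item 13) puts all analyses on an intention-to-treat sample, but does not mention feasibility or acceptability.

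**The concern.** Feasibility of a headset game is largely a fact about delivery: how many participants played as planned, for how long, and how often play was stopped or could not start. A satisfaction report, however well collected, does not measure this. Without a delivery outcome, a null result on e-cigarette use could not be told apart from a game that was not played for long enough.

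Acceptability raises a second question. The participants who tell most about whether a VR game is tolerable are those who felt ill, stopped or did not return. If the form reaches only those who complete, their view is lost and the reported figure may look better than it should. In Sub-study #2 the last assessment is the one after gameplay, so no later visit could recover a missed rating.

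**Working it through.** The plan states no feasibility threshold, completion rate or expected satisfaction, so there is no figure of its own to reproduce. The check has three parts.

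**1. Can the named measure answer the feasibility question?**

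| Question | Source named as a feasibility outcome |
|---|---|
| Satisfaction, gameplay experience | End-of-play self-report (both sub-studies) |
| Sessions attended, minutes played | None |
| Planned gameplay completed | None |
| Sessions stopped or not played for symptoms | None; the symptom check appears only as risk minimisation |

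Delivered exposure can vary within the wording itself. In Sub-study #2, one sitting gives 1 × 45-60 min = 0.75-1 hour and two give 2 × 45-60 min = 1.5-2 hours. A participant who plays once follows the one-or-two-sittings wording and receives half the stated total.

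**2. Who is asked?** The Measures paragraphs refer to the end of the gameplay period, which can mean a date that applies to every player. Section IV refers to completion of the intervention, which read literally applies to finishers. Item 11 describes players who may not complete and is silent on their assessment. The texts leave the matter open.

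**3. What could depend on it?** This is an illustration only; every rate is assumed. Let F be the proportion of finishers who find the game acceptable, N the same proportion among non-finishers, and m the proportion of players who do not finish and are not asked.

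- All-player acceptability = (1 − m) × F + m × N
- Overstatement = F − that value = m × (F − N)

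With F = 90%:

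| m | N | All-player figure | Overstatement |
|---|---|---|---|
| 10% | 0% | 0.90 × 0.90 = 81% | 9 points |
| 20% | 0% | 0.80 × 0.90 = 72% | 18 points |
| 10% | 50% | 81% + 5% = 86% | 4 points |
| 20% | 50% | 72% + 10% = 82% | 8 points |
| any | 90% | 90% | 0 |

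The overstatement is also 0 if m = 0, that is, if everyone is asked.

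For scale, the 95% half-width 1.96 × √(0.9 × 0.1 / n) is 5.5 points at n = 115 and 4.8 points at n = 150. Both sizes are shown because the plan enrols 300 (300 / 2 = 150 per arm if split equally) but lists two arms of 115 (115 + 115 = 230).

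**The case against.** A reader might infer that players who stop or miss sessions drop out of this outcome, that the denominator is confined to finishers, and that acceptability is therefore biased upward. The documents do not support that reading:

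- No text excludes these players, and the end of the gameplay period can be a time point for all of them.
- The rule in item 11 that "the research staff will immediately stop gameplay" ends play; it does not withdraw the participant.
- The bar on headset use applies while someone is tired or unwell, so the session might be rescheduled.
- The completion wording sits in a section on data handling and may be a loose way of saying after gameplay.
- Qualitative data on gameplay experience could pick up symptoms and stopping, and item 12 promises activity records.
- The 4-18 points rest on assumed rates, with a possible value of zero.

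All of this stands against a claim of demonstrated bias. It does not remove the narrower point. Intention-to-treat cannot supply a rating that was never collected. The item 12 records belong to safety monitoring, do not name gameplay minutes or stops, and are not linked to the aim. However the timing is read, self-report remains the only named measure of feasibility.

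It is also fair to say that the primary outcome is e-cigarette initiation, that no decision rule hangs on feasibility, and that counting non-responders in the denominator is one convention among several.

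**Conclusion.** The point holds in two parts of different strength. The first rests on the text alone: the only named measure cannot show whether the planned play was delivered, so the feasibility half of Aim 2b (Sub-study #1) and Aim 1b (Sub-study #2) is not answered by the stated method. The second is conditional: whether early stoppers and absentees are assessed is unspecified. If they are not, acceptability may be overstated, by nothing if they resemble finishers and by about 4-18 points under the assumed rates. The documents give no basis for choosing a value in that range, and going further to say that the plan restricts the outcome to finishers would be inference. The primary e-cigarette outcome is not threatened. The change is worth making before play begins, because session data not recorded at the time may not be recoverable.

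**What to change.** 1. In both Measures paragraphs, define feasibility from session records, building on those already promised in item 12. Use as denominator all participants assigned to Invite Only VR in Sub-study #1 and all who start it in Sub-study #2. Report the proportion completing the planned gameplay, minutes played, and the proportion with a session stopped or not played for symptoms.
2. Reconcile the 300 enrolled with the two arms of 115, so that the Sub-study #1 denominator is known.
3. Change Section IV, item 2 so that the existing satisfaction form is sought from every such participant whether or not they complete, at the last attended session if play ends early.
4. Report acceptability among responders with the number of non-responders beside it, plus a sensitivity figure that keeps non-responders in the denominator.

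The cost is a short log per participant and a changed trigger for an existing form. In Sub-study #2 the log would be a new task for school program staff, across 400 participants. The resulting figures may be less favourable. No change to the stopping or headset-use rules is proposed.

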Playing *Invite Only VR* may pose a potential psychological risk in that we address sensitive issues around tobacco use and its consequences. Research staff will be available to provide assistance to the participants, answer their questions, and serve as a resource if any distress or concern arises. The assessments and instruments may also present a potential risk given that some of the questions are sensitive in nature and address issues around substance use. Again, the Research staff will be available to assist the participants, the program sites staff, and the research staff members administering the assessments if there appears to be any distress around the questions being asked. If participants need additional or more intensive attention, [name] will provide consultation to the participant.

Also the use of a virtual reality headset for the project may pose a slight physical risks for the participants in the form of dizziness, queasiness, seizures (about 1 in 4000 experience this effect), eye or muscle twitching, and faintness.

11. **Minimizing Risks:** Describe the manner in which the above-mentioned risks will be minimized.

A number of precautions will be actively integrated into the research procedures to protect the confidentiality and anonymity of all participants. All research staff and the staff and volunteers participating in the intervention will be required to complete training in research ethics. Data collection forms will be designated by ID numbers only. A separate master file of names, addresses, contact persons, and telephone numbers, along with the study ID numbers will be maintained in a locked file cabinet in the P.I.'s research offices. All data entry and analyses will be completed with ID numbers only. The study will be explained to others, such as the guardian/parent and program staff as a study of child development that will focus on promoting healthy behaviors. In instances in which data are requested from other sources or it is beneficial to the participant to provide information to another individual or agency (e.g. medical personnel) this will only be done with the written permission of the guardian/parent on a "Release of Information" form stipulating

who the information is provided to, or received from. The research staff will follow standard confidentiality procedures for research programs.

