
This protocol presents minimal risks to the subjects and Unanticipated Problems Involving Risks to Subjects or Others (UPIRSOs), including adverse events, are not anticipated. In the unlikely event that such events occur, Reportable Adverse Events (which are events that are serious or life-threatening and unanticipated (or anticipated but occurring with a greater frequency than expected) and possibly, probably, or definitely related) or Unanticipated Problems Involving Risks to Subjects or Others that may require a temporary or permanent interruption of study activities will be reported immediately (if possible), followed by a written report within 5 calendar days of the Principal Investigator becoming aware of the event to the IRB via the RNI submission process in IRES IRB and any appropriate funding and regulatory agencies. The investigator will apprise fellow investigators and study personnel of all adverse events that occur during the conduct of this research project through regular study meetings and via email as they are reviewed by the principal

investigator. We will use procedures to detect and respond to adverse events that ensure prompt discovery of any adverse events and to minimize their effects. There is adequate surveillance and protections to discover adverse events promptly and keep their effects minimal. Data and safety monitoring procedures in this study include collection and monitoring of paper-based questionnaires and an organizational structure of clearly defined tasks assigned to all research personnel involved in the conduct of this study. We will keep a thorough record of research activities and completion of scheduled assessments.

- d. For multi-site studies for which the Yale PI serves as the lead investigator:
  - i. How will adverse events and unanticipated problems involving risks to subjects or others be reported, reviewed and managed? *Write here*
  - ii. What provisions are in place for management of interim results? *Write here*
  - iii. What will the multi-site process be for protocol modifications? *Write here*

13. **Statistical Considerations:** Describe the statistical analyses that support the study design.

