Statistical procedures and models for analyzing data have been selected according to the research hypotheses being investigated and the types of data available. In general, we will use two-tailed tests and p-values smaller than 0.05 will be considered to indicate statistical significance. When necessary, however, we will use appropriate adjustment of the level of significance (alpha) to account for multiple statistical tests. All statistical analyses will be conducted on an intention-to-treat sample using either SPSS/SAS statistical packages. Baseline characteristics will be analyzed using descriptive statistics.

We will evaluate the efficacy of Invite Only VR at reducing initiation of e-cigarette use (primary outcome). We will test the hypothesis that individuals who play Invite Only VR will be less likely to report the initiation of e-cigarette use in comparison to the control condition. We will conduct a longitudinal analysis using a linear mixed models approach to compare participants in the intervention group to participants in the control group on e-cigarette use from baseline across all follow-up assessments. An advantage of mixed models is that participants with missing data need not be excluded as all available data are used in estimating parameters. We will also use logistic regression models to determine if any relevant baseline variables are associated with rates of initiation of e-cigarette use (constructed as a binary outcome (Yes/No). We plan to evaluate the prognostic significance of a small set of predictor variables (e.g., knowledge, intentions, perceptions, attitudes, social norms, and self efficacy) and use them as covariates in the primary analysis.

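### The protocol states inconsistently how the RCT collects its self-reported primary outcome: interview by staff in one section, entry by the participant in another

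*Combined protocol and SAP*

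**What the plan says.** All references are to the combined protocol and SAP.

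- **Section I, item 4, Sub-study #1, Measures:** "All assessments will be conducted via face-to-face interviews with a research assistant and each adolescent". No item is exempted. The paragraph covers intentions, refusal self-efficacy, norms, attitudes and smoking behaviour at baseline, after gameplay, and at 3 and 6 months.
- **Section IV, Confidentiality & Security of Data, item 2:** "Research staff will enter the data into the OnCore system", followed by "For the more sensitive information collected, the participant will enter these data". The items, sub-study and visits are not specified.
- **Section I, item 10, Risks:** "some of the questions are sensitive in nature and address issues around substance use". By the protocol's own description, the use questions are among the sensitive ones.
- **Section I, item 12, Data and Safety Monitoring Plan:** refers to "collection and monitoring of paper-based questionnaires".
- **Section I, item 13, Statistical Considerations:** initiation of e-cigarette use is the primary outcome, and the hypothesis is that "individuals who play Invite Only VR will be less likely to report the initiation of e-cigarette use in comparison to the control condition".
- **Section I, item 4, Sub-study #2, Measures:** the second sub-study collects much the same constructs on a Qualtrics website.

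The documents describe no blinding of the person who collects the data and no biochemical check on reported use.

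**The concern.** The primary result rests on what each adolescent says about e-cigarette use. A site reading the Measures paragraph would ask the question in an interview. A site reading the data-security section would hand over the device for that item. Both would be following the protocol, and the mode could vary between visits or staff.

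The mode matters because a young adolescent may be reluctant to admit vaping to an adult face to face. There are two consequences:

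- If reluctance is the same in both arms, reported events fall and power falls with them, but the test keeps its 5% error rate.
- If reluctance is greater among those who have played a game designed to discourage e-cigarettes, reported initiation is lower in that arm even when true initiation is not.

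Neither intention-to-treat analysis nor the planned mixed model corrects this. The protocol offers the mixed model as a way of handling missing data, not misreported data.

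**Working it through.** **1. Is the mode settled by the text?**

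| Place | Mode stated | Scope stated |
|---|---|---|
| Item 4, Sub-study #1, Measures | In-person interview by a research assistant | All RCT assessments |
| Section IV, item 2 | Participant enters sensitive data; staff enter the rest | No items, sub-study or visits named |
| Item 12, monitoring plan | Paper questionnaires | General |

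Item 10 treats substance-use questions as sensitive, so the e-cigarette item plausibly falls under participant entry. The Measures paragraph exempts nothing, so it also falls under interview. The first two rows conflict on the item that matters most. The third adds little, because an interviewer can fill in a paper questionnaire.

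The Measures paragraph names smoking behaviour rather than e-cigarette initiation. The link to the primary outcome comes from item 13 together with the statement that all assessments are interviews.

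**2. What could misreporting do?**

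The plan gives no initiation rate, effect size or power, so there is no figure to reproduce. The true rates and reporting proportions below are assumptions. The arm sizes are 115 (stated in item 4) and 150 (300 enrolled, if split equally); that mismatch is a separate matter. The test is a simple two-sided comparison of two proportions at 0.05, used in place of the planned mixed model.

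Observed rate = true rate × proportion of initiators who report it.

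*Unequal reporting, no true effect, true initiation 10% in both arms:*

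- 80% v 70% reported: 0.10 × 0.80 = 0.08 and 0.10 × 0.70 = 0.07; risk ratio 0.07/0.08 = 0.875, or 0.88.
- 80% v 60% reported: 0.08 and 0.10 × 0.60 = 0.06; risk ratio 0.06/0.08 = 0.75.

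The true rate cancels, so the ratio depends only on the two reporting proportions. In counts, 8% v 6% is 9.2 v 6.9 reported events with 115 per arm, and 12 v 9 with 150 per arm.

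Probability of a significant result = Φ((d − 1.96·s0)/s1) + Φ((−d − 1.96·s0)/s1), where d is the difference in observed rates, s0 the pooled standard error and s1 the unpooled one. For 8% v 6% with 115 per arm:

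- s0 = √(0.07 × 0.93 × 2/115) = 0.0336
- s1 = √((0.08 × 0.92 + 0.06 × 0.94)/115) = 0.0336
- Φ(−1.37) + Φ(−2.56) = 0.086 + 0.005 = 0.091

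The same formula gives:

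| Reported, control v VR | Risk ratio | 115 per arm | 150 per arm |
|---|---|---|---|
| 80% v 70% | 0.88 | 6.0% | 6.2% |
| 80% v 60% | 0.75 | 9.1% | 10.4% |
| 90% v 70% | 0.78 | 8.6% | 9.8% |

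Over a wider grid (true initiation 5% to 20%, control reporting 90%, VR reporting 80% down to 50%), the risk ratio runs from 0.89 to 0.56. The rejection rate runs from 5.4% to 41.6% with 115 per arm, and from 5.5% to 51.5% with 150.

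*Equal reporting, true initiation 10% v 5%:* if reporting falls from 100% to 70% in both arms, observed rates become 7% v 3.5%. Power falls from 30% to 22% with 115 per arm, and from 37.5% to 27% with 150. The error rate under no effect stays at 5%.

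**The case against.** The best defence is that the two statements describe different things. The Measures paragraph describes the session; the data-security section describes how answers are recorded. An adolescent could key in sensitive answers during a one-to-one session, which would satisfy both. That is a reasonable reading, and it means a reader should not infer that the primary item is certainly asked aloud, or that the modes cannot be reconciled. The protocol does not state this arrangement, however, so the conflict remains until it does.

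A second objection concerns bias between arms. A reader might infer that interviewing will itself produce a false preventive effect. The documents do not support that:

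- Any extra reluctance in the game arm would come from exposure to the game and knowledge of allocation, and some would persist under private self-entry.
- The pressure should be strongest just after gameplay, whereas new initiation would accrue mainly by 3 and 6 months.
- Participants are given one neutral description of the study's purpose, whatever their arm.

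These points stand. They make the differential effect a risk of unknown size. Interview mode may enlarge it, and the plan describes nothing that limits it.

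Third, the magnitudes are assumed, and in the milder cases a spurious significant result is unlikely (about 6%). That is also correct. The estimate would still be biased at those settings, and in a pilot meant to give preliminary evidence the estimate is itself of interest.

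**Conclusion.** The point holds as an unresolved inconsistency in how the self-reported primary outcome is collected, with a real but unquantified risk of under-reporting if the interview wording is followed. The inconsistency rests on the text alone. The size of any bias rests on assumption: with no true effect, an apparent risk ratio of 0.88 (80% v 70% reporting) or 0.75 (80% v 60%), and a false-positive rate of about 6% to 10% for those two cases rather than 5%. Under-reporting that is equal in the two arms would cost power only. The text should be settled before data collection, because analysis cannot recover use that was never reported.

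**What to change.** Amend the Sub-study #1 Measures paragraph so that e-cigarette and tobacco use items, and any other items the protocol regards as sensitive, are completed privately by the participant. The mode should be the same in both arms at baseline, post-gameplay, 3 months and 6 months, with the research assistant on hand for help. List those items. Bring Section IV, item 2 and the monitoring plan in item 12 into line. It would also help to state whether the staff who collect data know the allocation.

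The cost is small. Participant entry is already foreseen in Section IV, and sub-study #2 already collects its assessments on Qualtrics. The losses are some opportunity to clarify questions and the work of laying out the use-history measure for self-administration (the source cited for smoking behaviour is a timeline follow-back method). Self-entry will reduce reporting bias that comes from knowing the allocation but will not eliminate it, so the report should still list self-report as a limitation.
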